## 7.3. Lost to Follow-up

A participant will be considered lost to follow-up if he or she repeatedly fails to return for scheduled visits and is unable to be contacted by the study site.

The following actions must be taken if a participant fails to return to the clinic for a required study visit:

- The site must attempt to contact the participant and reschedule the missed visit as soon as possible and counsel the participant on the importance of maintaining the assigned visit schedule and ascertain whether or not the participant wishes to and/or should continue in the study.

- Before a participant is deemed lost to follow up, the Investigator, or designee, must make every effort to regain contact with the participant (where possible, 3 telephone calls and, if necessary, a certified letter to the participant's last known mailing address or local equivalent methods). These contact attempts should be documented in the participant's medical record.
- Should the participant continue to be unreachable, he/she will be considered to have withdrawn from the study.
- If a participant is deemed lost to follow-up, information about survival status at time of discontinuation and at Week 52 should be collected, whenever possible. If a participant's survival status is not available at the time, sites should attempt to collect the status (eg, via public records or telephone call).

Discontinuation of specific sites or of the study as a whole are handled as part of Section [10.1.8](#).

## **8. STUDY ASSESSMENTS AND PROCEDURES**

- Study procedures and their timing are summarized in the Schedules of Activities (Section 1.3). Protocol waivers or exemptions are not allowed.
- Immediate safety concerns should be discussed with Alexion immediately upon occurrence or awareness to determine if the participant should continue or discontinue study intervention.
- Adherence to the study design requirements, including those specified in the Schedules of Activities (Section 1.3), is essential and required for study conduct.
- All screening evaluations must be completed and reviewed to confirm that potential participants meet all eligibility criteria. The Investigator will maintain a screening log to record details of all participants screened and to confirm eligibility or record reasons for screening failure, as applicable.
- Procedures conducted as part of the participant's routine clinical management (eg, blood count) and obtained before signing of the ICF may be utilized for screening or baseline purposes provided the procedures met the protocol-specified criteria as described in Section 5.
- The Investigator may delegate activities as permissible and documented in site delegation log.

### **8.1. General Assessments and Procedures**

#### **8.1.1. Informed Consent**

The Investigator or qualified designee must obtain a signed and dated ICF for each participant and/or their legally authorized representative prior to conducting any study procedures. The process for informed consent is outlined in Section 10.1.3. All efforts should be made to ensure participants are willing to comply with study participation prior to conducting the Screening procedures.

#### **8.1.2. Inclusion/Exclusion Criteria**

All inclusion (Section 5.1) and exclusion (Section 5.2) criteria must be reviewed by the Investigator or qualified designee to ensure the participant qualifies for study participation.

#### **8.1.3. Demographics**

Demographic parameters, including age, sex, race, and ethnicity will be documented in the CRF.

#### **8.1.4. Medical History**

The participant's relevant medical history, including prior and concomitant conditions/disorders (including TMA diagnosis), treatment history, and family history of relevant diseases will be evaluated at Screening by the Investigator, or qualified designee, and documented in the source documents and CRF. Any changes to medical history occurring during the Screening Period and prior to first dose of study drug on Day 1 will be documented prior to study drug administration.

### **8.1.5. Vaccination and Antibiotic Prophylaxis**

Due to its mechanism of action, the use of ravulizumab increases a participant's susceptibility to meningococcal infection due to *N meningitidis*. To reduce the risk of infection, all participants must be vaccinated within 3 years prior to or at the time of the first infusion of study drug. Participants who have not been vaccinated prior to starting study drug for any reason, should receive appropriate prophylactic antibiotics prior to and for at least 2 weeks after vaccination. Vaccines against serotypes A, C, Y, W135, and B where available, are recommended in preventing the commonly pathogenic meningococcal serotypes. Participants must receive the complete primary vaccination series and be revaccinated if indicated according to current national vaccination guidelines. Vaccination may not be sufficient to prevent meningococcal infection.

Participants should be administered prophylactic antibiotics for meningococcal infection until at least 2 weeks after vaccination if randomization occurs < 2 weeks after initial vaccination. Consideration should be given per official guidance and local practice on the appropriate use of prophylactic antibacterial agents. All participants should be monitored for early signs of meningococcal infection, evaluated immediately if infection is suspected, and treated with appropriate antibiotics, if necessary. Participants who cannot receive meningococcal vaccine should receive antibiotic prophylaxis coverage against *N meningitis* during the entire Treatment Period and for 8 months following the final dose of study drug.

To increase risk awareness and promote quick disclosure of any potential signs or symptoms of infection experienced by the participants during the course of the study, participants will be provided a Participant Safety Card to carry with them at all times (Section 8.3.1). Additional discussion and explanation of the potential risks, signs, and symptoms will occur at specific time points as part of the review of the Participant Safety Card and throughout the study as described in the Schedule of Activities.

Meningococcal serogroups ACWY and B vaccinations are required during screening for participants who do not meet criteria for previous vaccination. The vaccination series will be completed during the study according to national and local vaccination schedule guidelines.

Participants who have TMA associated with triggers of lupus nephritis, systemic sclerosis, or solid organ transplant must also be vaccinated against *Hib* and *S pneumoniae* prior to randomization, unless previously vaccinated, if indicated according to current national/local vaccination guidelines.

Vaccination status and administration of any vaccines, including those for *N meningitidis*, will be recorded on the CRF.

## **8.2. Efficacy Assessments**

### **8.2.1. Laboratory Assessments for Efficacy Endpoints**

Laboratory assessments (platelets, LDH, and eGFR) to determine Complete TMA Response, Hematologic Response, and Renal Response will be performed according to the Schedule of Activities (Section 1.3) and will be assessed based on the predetermined criteria for TMA response as defined in Section 3.2.

The eGFR calculation will be based on the CKD-EPI formula for all participants using serum creatinine collected prior to study drug administration, if applicable.

#### **8.2.2. Dialysis Status**

Participant dialysis status  $\leq$  14 days prior to Screening, during the Screening Period, and during the study will be documented on the CRF.

#### **8.2.3. Transfusion History and Transfusion Requirement Status During the Study**

The number and volume of transfusions  $\leq$  14 days prior to Screening, during the Screening Period, and during the study will be documented on the CRF. The information to be collected includes date of the transfusion, number of units, and volume of each blood component given.

#### **8.2.4. Survival Status**

Participant survival status will be assessed throughout the duration of the study.

### **8.3. Safety Assessments**

#### **8.3.1. Participant Safety Card**

Before the first dose of the study drug, a Participant Safety Card will be provided to participants to carry with them at all times until 8 months after the final dose of study treatment. The card is provided to increase participant awareness of the risk of meningococcal infection and promote quick recognition and disclosure of any potential signs or symptoms of infection experienced during the course of the study and to inform participants on what actions must be taken if they are experiencing signs or symptoms of infection.

At each visit throughout the study, the study staff will ensure that the participant has the Participant Safety Card.

#### **8.3.2. Physical Examinations**

- A complete physical examination will include, at a minimum, assessments of the following organs/body systems: skin, head, ears, eyes, nose, throat, neck, lymph nodes, chest, heart, abdomen, extremities, musculoskeletal, and neurological state (with emphasis on presence/degree of edema).
- An abbreviated physical examination will include, at a minimum, a body-system relevant examination based upon the Investigator's judgment and participant symptoms.
- Investigators should pay special attention to clinical signs related to previous serious illnesses.
- Additional physical examinations can be performed as medically indicated during the study at the Investigator's discretion.
- Weight and height (Screening only) will also be measured and recorded.

### **8.3.3. Vital Signs**

- Body temperature (°C or °F), heart rate, respiratory rate, systolic and diastolic blood pressure (mm Hg), and pulse oximetry will be assessed.
- Blood pressure and heart rate measurements will be assessed with the participant in a seated or supine position using a completely automated device. Manual techniques will be used only if an automated device is not available.
- Blood pressure and heart rate measurements should be preceded by at least 5 minutes of rest for the participant in a quiet setting without distractions (eg, television, cell phones). Ideally, the same arm for each participant should be used for measurements.
- Vital signs will be collected predose at ravulizumab dosing visits.

### **8.3.4. Electrocardiograms**

- Single 12-lead electrocardiogram (ECGs) will be conducted locally to obtain heart rate, PR, QRS, interval between the start of the Q wave and the end of the T wave in an ECG (QT), and corrected QT (QTc) intervals. QT interval will be corrected for heart rate using Fridericia's formula (QTcF).
- Single 12-lead ECG will be performed at Screening and at the end of the Treatment Period (Day 183). For participants that discontinue study drug prior to Week 26, an ECG should be performed at the ED Visit.
- Participants must be supine during ECG collection.
- The Investigator will be responsible for reviewing the ECG to assess whether the ECG is within normal limits and determine the clinical significance of the results.

### **8.3.5. Clinical Safety Laboratory Assessments**

- All protocol-required laboratory assessments, as outlined in Section 10.2, must be conducted in accordance with the Laboratory Manual and the Schedule of Activities (Section 1.3).
- The Investigator must review the laboratory report, document this review, and record any clinically relevant changes occurring during the study in the AE section of the CRF. The laboratory reports must be filed with the source documents. Clinically significant abnormal laboratory findings are those which are not associated with the underlying disease, unless judged by the Investigator to be more severe than expected for the participant's condition.
- All laboratory tests with values considered clinically significantly abnormal during participation in the study should be repeated until the values return to normal or baseline or are no longer considered clinically significant by the Investigator.

Note: For participants that withdraw from the study, all laboratory tests with values considered clinically significantly abnormal within 8 weeks after the last dose of study drug should be repeated until the values return to normal or baseline or are no longer considered clinically significant by the Investigator.

### **8.3.5.1. Virus Serology**

Human immunodeficiency virus testing for HIV-1 and HIV-2 is required for all participants prior to randomization.

### **8.3.6. Pregnancy**

- Pregnancy testing must be performed on all women of childbearing potential (WOCBP) at protocol-specified time points in the Schedule of Activities (Section 1.3). Pregnancy tests (urine or serum) may also be performed at any time during the study at the Investigator's discretion.
- A negative pregnancy test is required for WOCBP before study drug administration.
- Pregnancy data from female participants and female spouses/partners of male participants will be collected from the first dose of study drug through the EOS Visit. Any female participant who becomes pregnant while participating in the study will be discontinued from study drug. If a pregnancy is reported, the Investigator, or designee, must immediately inform Alexion within 24 hours of awareness of the pregnancy and follow the procedures outlined in Section 10.6.3.

## **8.4. Adverse Events and Serious Adverse Events**

The definitions of AEs and SAEs can be found in Section 10.4

All AEs will be reported to the Investigator or qualified designee by the participant (or, when appropriate, by a caregiver, surrogate, or the participant's legally authorized representative).

The Investigator and any qualified designees are responsible for detecting, documenting, and recording events that meet the definition of an AE or SAE and remain responsible for following up AEs that are serious, considered related to the study drug or study procedures, or that caused the participant to discontinue the study drug (see Section 7).

Procedures for recording, evaluating, follow-up, and reporting AEs and SAEs are outlined in Section 10.4.

### **8.4.1. Time Period and Frequency for Collecting AE and SAE Information**

All AEs and SAEs will be collected from the signing of the ICF until the EOS Visit. For participants who withdraw from the study during the Treatment Period, all AEs and SAEs should be collected through 8 weeks after last dose of study drug. For participants who discontinue study drug, but remain in the Follow-up Period, all AEs and SAEs will be collected through the EOS Visit.

All SAEs will be recorded and reported to Alexion or the designee immediately and under no circumstance should this exceed 24 hours, as indicated in Section 10.4. The Investigator, or designee, will submit any updated SAE data to Alexion within 24 hours of the date the study site became aware of the event.

Investigators are not obligated to actively seek AE or SAE data after conclusion of the study participation. However, if the Investigator learns of any SAE, including a death, at any time after a participant has concluded participation in the study, and he/she considers the event to be

reasonably related to the study drug or study participation, the Investigator must promptly notify Alexion.

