**Table 1: Schedule of Activities for Screening and 26-Week Treatment Period**

Period	Screening	Treatment Period													Notes
Visit		1	2	3	4	5	6	7	8	9	10	11	12	13	
Week	Up to 2 W		W1	W2	W3	W4	W6	W8	W10	W12	W14	W18	W22	W26/ED a	
Days and Window	D -14 to -1	D1	D8 ± 2	D15 ± 2	D22 ± 2	D29 ± 2	D43 ± 2	D57 ± 2	D71 ± 3	D85 ± 3	D99 ± 3	D127 ± 3	D155 ± 3	D183 ± 3	
Blood and urine samples for RTCA		X h	X		X			X		X		X		X	All sites are to collect and ship frozen RTCA plasma and urine samples to the central laboratory. Only selected sites will perform additional on-site testing of freshly collected blood, plasma and urine using a dedicated RTCA reader and specific instructions provided by the Sponsor and as defined in the laboratory manual. See Section 8.9.3
Blood sample for genetic testing i		X i													May be collected anytime during study
Study Intervention															
Randomization		X													
Ravulizumab or placebo		X		X					X			X			Administer after all other required tests/procedures.

Note: All assessments should be performed prior to administration of study drug on dosing days, unless otherwise specified. For participants on dialysis, study visits should be conducted on non-dialysis days, whenever possible. However, if this is not feasible, then all study-related procedures and study drug administration should be performed prior to the participant receiving dialysis.

a For participants who discontinue study drug prior to the end of the Treatment Period, the ED visit should be completed as soon as possible. In addition, a Follow-up Phone Call will be performed 8 weeks (56 days) ± 5 days following the participant's last dose of study drug to collect concomitant medications, nonpharmacologic therapies and procedures, and AEs.

b Weight should be obtained at every visit and measured predose on dosing visits. The dose regimen is based on the last recorded study visit body weight. If the study drug is prepared the day before a visit, the weight from the previous study visit may be used.

c Vital sign measurements include systolic and diastolic BP, pulse oximetry, heart rate, respiratory rate, and body temperature. On dosing days, vital signs will be taken predose.

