**Table 3: Potential Risks and Mitigation Strategies**

Risks of Clinical Significance	Summary of Data/Rationale for Risk	Mitigation Strategy
Identified risk		
Meningococcal infection	Complement C5 inhibition is known to increase the susceptibility to infections caused by N meningitidis .	Participants must be vaccinated against all available serotypes of N meningitidis (A, C, Y, W 135, and B) where available. If participants cannot be vaccinated, they should be administered prophylactic antibiotics for the entire period they are treated with ravulizumab and for 8 months following their last dose of ravulizumab. Once the participant is able to be vaccinated, antibiotic prophylaxis for meningococcal infections should be maintained for at least 2 weeks after vaccination. However, vaccination may not be sufficient to prevent meningococcal infection.
Potential risks		
Serious infection	
Apart from the predictable risk of infection with Neisseria species, which is well-known and directly related to the mechanism of action of ravulizumab, the mechanism that may lead to other serious infections in patients treated with ravulizumab remains unclear.
 
Since the relevance of serious infection with ravulizumab therapy has not been confirmed in clinical trials, this remains a potential risk.
	Increased awareness of healthcare professionals and participants about the potential risk of serious infection. Monitoring for signs and symptoms of serious infections will be conducted as part of routine safety assessments for this study.
Immunogenicity	
Treatment with any therapeutic protein has the potential to induce an immune response. Potential clinical consequences may include hypersensitivity type reactions, decrease in efficacy, and induction of autoimmunity, including antibodies to the endogenous form of the protein (Casadevall, 2002; Li, 2001).
 
Protein therapies administered intravenously have the potential risk of causing local (infusion-site) reactions and systemic reactions (infusion-associated reactions).
	
In Studies ALXN1210-PNH-103 and ALXN1210-PNH-201, no participant had a positive ADA sample. In Phase 3 studies in PNH (N = 261) and aHUS (N = 89) patients, there were 2 (0.57%) cases of treatment-emergent ADAs reported with ravulizumab.
 
Presence of ADA will be assessed. Monitoring for infusion reactions will be conducted as part of routine safety assessments for this study.

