## 7.2. Participant Withdrawal from the Study

- All efforts should be made to ensure participants are willing to comply with study participation prior to conducting the screening procedures.
- The study staff should notify Alexion and their site monitor of all study withdrawals as soon as possible. The reason for participant discontinuation must be recorded in the source documents and CRF.
- A participant may withdraw from the study at any time at his/her own request, or may be withdrawn at any time at the discretion of the Investigator for safety, behavioral, compliance, or administrative reasons.
- For participants who withdraw from the study prior to Week 26, an ED Visit should be conducted, whenever possible, per the Schedule of Activities (Section 1.3). A Safety Follow-up Phone Call should be conducted at least 8 weeks after the final dose of study drug to collect information on concomitant medications, nonpharmacologic therapies and procedures, and AEs.
- For participants who withdraw from the study during the Follow-up Period, an EOS Visit should be conducted, whenever possible, per the Schedule of Activities (Section 1.3).
- The participant will be permanently discontinued from the study drug at the time of study withdrawal.
- If the participant withdraws consent for disclosure of future information, Alexion may retain and continue to use any data collected before such a withdrawal of consent, if permitted by local requirements.
- If a participant withdraws from the study, the participant may request destruction of any samples taken and not tested, and the Investigator, or designee, must document this in the site study records.
- Information about survival status at time of discontinuation and at Week 52 should be collected, whenever possible. If a participant's survival status is not available at the time of discontinuation, sites should attempt to collect the status (eg, via public records or telephone call).

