#### **9.4.2.1. Adverse Events**

The following definitions will be used for AEs:

- Pretreatment AEs: Any AE that starts after providing informed consent, but before the first infusion of study drug
- Treatment-emergent adverse event (TEAE): Any AE that starts between the start of the first infusion of study drug and up to 8 months after the last infusion of study drug

- Treatment-emergent SAE (TESAE): A TEAE that meets the criteria for serious (Section 10.4.2)
- Post-treatment AEs: Any AE that starts 8 months or later after the last infusion of study drug

The incidence of TEAEs, TEAEs leading to withdrawal from the study, TEAEs leading to study drug discontinuation, and TESAEs will be summarized by treatment group. All AEs will be coded using the Medical Dictionary for Regulatory Activities (MedDRA), version 23.0 or higher, and will be summarized by System Organ Class and Preferred Term overall, by severity, and by relationship to study drug.

Detailed by-participant listings of TEAEs, TESAEs, related TEAEs, TEAEs leading to withdrawal from the study, and TEAEs leading to study drug discontinuation will be provided.

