#### **10.6.2.1. Guidance for Female Participants**

Female participants of childbearing potential must have a negative serum pregnancy test as required by local regulations within 2 weeks prior to the first dose of study drug and have a negative urine pregnancy test prior to the first dose of study drug on Day 1. Additional requirements for pregnancy testing during and after dosing with study drug are indicated in the Schedule of Activities (Section 1.3).

The Investigator is responsible for the review of medical history, menstrual history, and recent sexual activity to decrease the risk for inclusion of a woman with an early undetected pregnancy.

The Investigator should evaluate the potential for contraceptive method in relationship to the first dose of study drug.

Female participants of childbearing potential must use a highly effective or acceptable method of contraception, including at least 1 of the following until at least 8 months (generally 5.5 terminal half-lives) after the final dose of study drug. Highly effective methods are:

1. Intrauterine device in place for at least 6 weeks prior to first dose of study drug.
2. Progestogen-only hormonal contraception associated with inhibition of ovulation (either oral, injectable, or implantable) for at least 6 weeks prior to first dose of study drug.
3. Intrauterine progestogen releasing system for at least 6 weeks prior to first dose of study drug.
4. Bilateral tubal occlusion for at least 6 weeks prior to first dose of study drug.
5. Combined (estrogen- and progestogen-containing) hormonal contraception (either oral, intravaginal, or transdermal) for at least 6 weeks prior to first dose of study drug.
6. Surgical sterilization of the male partner (medical assessment of azoospermia is required if vasectomy was performed within the prior 6 months prior to the first dose of study drug). Male partner is still required to use condom during sexual intercourse.
7. Sexual abstinence for female participants:
  - Sexual abstinence is considered a highly effective method only if defined as refraining from heterosexual intercourse. In this study, abstinence is only acceptable if consistent with the participant's preferred and usual lifestyle. Abstinent female participants must refrain from heterosexual intercourse for at least 8 months after the final dose of study drug.

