This was a Phase 3, randomized, double-blind, placebo-controlled study of ravulizumab in addition to best supportive care (BSC) in adult participants (\geq 18 years of age) with thrombotic microangiopathy (TMA) following a defined trigger. All participants had severe acute kidney injury and a diagnosis of TMA based on protocol-defined criteria (ie, thrombocytopenia, microangiopathic hemolytic anemia, and elevated lactate dehydrogenase [LDH]), which was associated with at least 1 trigger, such as autoimmune, infection, solid organ transplant, drugs, or malignant hypertension, occurring \leq 14 days prior to randomization.

The study consisted of an up to 2-week Screening Period, a 26-week randomized Treatment Period, and a 26-week Post-treatment Follow-up Period. Thus, the total treatment duration was 26 weeks, and the total study duration was up to 54 weeks.

Participants were screened for eligibility for up to 2 weeks during the Screening Period. Approximately 100 adult participants were planned to be randomized in a 1:1 ratio to receive either ravulizumab or placebo. Randomization was stratified by baseline dialysis status and by primary trigger type.

During the 26-week Treatment Period, all participants received a weight-based loading dose of ravulizumab or placebo on Day 1, followed by weight-based maintenance doses of ravulizumab or placebo on Day 15 and then once every 8 weeks (q8w) thereafter. All participants received BSC throughout the study.

During the 26-week Post-treatment Follow-up Period, participants continued to receive BSC at the discretion of the Investigator and will be monitored for safety, TMA response, and clinical events of interest.

The end of the study was defined as the last participant's last visit in the Post-treatment Follow-up Period.

Enrollment in the study was closed, and the decision to terminate the study when the last participant in treatment has completed the 26-week Treatment Period was made on 24 Oct 2022.

Disclosure Statement: This was a parallel group treatment study with 2 arms that was participant, Investigator, and outcomes assessor blinded.

Number of Participants: It was planned that approximately 100 participants would be enrolled in the study. A total of 16 participants were enrolled in the study.

Intervention Groups and Duration:

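### Adverse events of participants who leave early are actively collected for 8 weeks after the last dose, but counted as treatment-emergent for 8 months over a denominator that treats these participants as fully observed

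*Protocol*

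**What the plan says.** **Collection.** The limit in Protocol 8.4.1 opens with "For participants who withdraw from the study during the Treatment Period" and then states that "all AEs and SAEs should be collected through 8 weeks after last dose of study drug". The same section follows participants who stop drug but stay in the study to the End of Study Visit. Once participation has ended, sites need not look for events, but must report any SAE they learn of and consider reasonably related.

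**The call.** Three places describe it differently:
- Protocol 7.2 (withdrawal): "A Safety Follow-up Phone Call should be conducted at least 8 weeks after the final dose of study drug", with no upper limit.
- Table 1 footnote a, written for everyone who stops study drug early: "a Follow-up Phone Call will be performed 8 weeks (56 days) ± 5 days following the participant's last dose of study drug", in addition to an Early Discontinuation Visit.
- Protocol 7.1: every effort is made to keep those who stop drug in the study to Week 52. The Early Discontinuation Visit and 8-week call are only for those who decline further visits.

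**Counting.** Protocol 9.4.2.1 defines treatment-emergent as "up to 8 months after the last infusion of study drug"; SAP 7.7.2 and 9.3.8 use the same limit. SAP 7.7.2 bases percentages on treated participants in the Safety Set. SAP 7.7.2.4 gives MACE per 100 patient-years, with patient-years of follow-up.

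**Termination.** SAP Section 4 records "the decision to terminate the study when the last participant in treatment has completed the 26-week Treatment Period".

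**The concern.** The protocol collects over one window and counts over another, and neither document reconciles them. The 8 months is not arbitrary. The safety card runs to 8 months. Contraception runs for "at least 8 months (generally 5.5 terminal half-lives) after the final dose of study drug". Meningococcal prophylaxis, for participants who cannot be vaccinated, continues "for 8 months following their last dose of ravulizumab". The visit schedule also follows completers for close to 8 months. Early leavers are the exception.

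A participant who leaves early contributes a full unit to the denominator of every TEAE percentage, while most of the window after the last dose is never asked about. An unsolicited event is then indistinguishable from no event, so incidence is understated. The understatement is unequal between arms if withdrawal is unequal. The events most easily missed are non-serious AEs and SAEs that never reach the site, such as an infection treated elsewhere.

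**Working it through.** **Inputs**
- Collection limit: 8 weeks (Protocol 8.4.1), given as 56 ± 5 days in Table 1 footnote a.
- Treatment-emergent limit: 8 months (Protocol 9.4.2.1; SAP 7.7.2, 9.3.8).
- Dosing days: 1, 15, 71 and 127 (Table 7).
- Week 26 visit: Day 183 (Table 1). End of Study: Day 365 ± 7 (Table 2).
- Days per month are not given. I assume 30.4375, with a range of 28 to 31.

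**Step 1. Reproduce the plan's figure.** 8 × 7 = 56 days, which agrees with footnote a.

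**Step 2. Length of 8 months.** 8 × 30.4375 = 243.5 days (range 8 × 28 = 224 to 8 × 31 = 248).

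**Step 3. Share of the post-last-dose window not actively collected.** 1 − 56/243.5 = 77.0%, or 243.5 − 56 = 187.5 days. With 28-day months it is 75.0%, with 31-day months 77.4%. Over the ± 5-day call window at 243.5 days it runs from 1 − 61/243.5 = 74.9% to 1 − 51/243.5 = 79.1%.

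**Step 4. Share of the whole window from first dose.** For last dose on Day d: 187.5 / ((d − 1) + 243.5).

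| Last dose | Collection limit (d + 56) | Share not actively collected |
|---|---|---|
| Day 1 | Day 57 | 187.5/243.5 = 77% |
| Day 15 | Day 71 | 187.5/257.5 = 73% |
| Day 71 | Day 127 | 187.5/313.5 = 60% |
| Day 127 | Day 183 | 187.5/369.5 = 51% |

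The first three limits fall before Day 183, so for those participants even the endpoint of AE incidence by Week 26 can be incompletely observed. The table assumes that the participant leaves before the 56 days have run; someone who misses doses and leaves later is observed until leaving.

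**Step 5. Completers.** 365 − 127 = 238 days, and 238/243.5 = 98% (95% to 101% over the ± 7-day visit window).

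**Step 6. Termination.** 183 − 127 = 56 days. A fully dosed participant whose observation stops at Day 183 has the same 56 days as an early leaver.

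**Step 7. The documents' own half-life.** 8 months as 5.5 half-lives implies 243.5/5.5 = 44.3 days. At 56 days, 56/44.3 = 1.26 half-lives have passed and 0.5^1.26 ≈ 42% of drug would remain. This assumes simple exponential decay and concerns only the ravulizumab arm.

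**The case against.** The strongest reply is that 8 weeks is a deliberate and consistent rule for people who have left. Protocol 7.1, 7.2, 8.4.1 and footnote a all use it, and so does Section 8.3.5 for repeating abnormal laboratory tests after withdrawal. Reporting does not stop entirely, and Week 52 survival is sought where possible. Consent may limit contact. No treatment comparison will be tested, and 16 participants were enrolled. All of this stands, and it limits the severity. It does not explain why events are counted over a window in which these participants are not asked about them.

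Stronger readings that a reader might infer, and that the documents do not support:
- *That 8 months is the period in every risk statement.* Section 8.3.5 uses 8 weeks, and 8-month prophylaxis applies only to those who cannot be vaccinated.
- *That everyone who stops drug is lost at 8 weeks.* Those who remain are followed to End of Study, and Section 8.4 keeps the investigator responsible for following AEs that led to stopping. The gap is therefore not a general loss of toxicity data. Withdrawal during the Follow-up Period is also outside the 8-week clause.
- *That pregnancies are cut off at 8 weeks.* They have their own window, first dose to the End of Study Visit (8.3.6, 10.6.3), and a participant's pregnancy is followed to outcome even after withdrawal (10.6.3.2).
- *That about 10 of 100 participants are affected.* The 10% in Protocol 9.2 is a drop-out assumption in the power calculation, not a forecast of Treatment Period withdrawals.
- *That one arm is biased in a known direction.* Withdrawal by arm is not given.

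**Conclusion.** The mismatch is real and should be fixed, though it does not undermine the trial. For participants who withdraw during the Treatment Period, or who stop drug and decline visits, about 77% of the treatment-emergent window after the last dose is not actively ascertained (75% to 77% across month lengths). Of the whole window from first dose the share is 51% to 77%. They nevertheless count in the denominator as if fully observed. Termination puts the last participants at Day 183 in the same position, on the reading that AE collection ends with the study; SAP 7.7.2.4 still plans MACE rates to Day 365, so the SAP should say which holds.

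How many participants are affected, and whether the arms differ, cannot be determined from the documents. If the 16 participants split 8 and 8, one missed event would shift an arm's percentage by 1/8 = 12.5 points.

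**What to change.** 1. **Protocol 7.1, 7.2, 8.4.1 and Table 1 footnote a.** Reconcile the collection period for early leavers with the 8-month treatment-emergent window. Keep the 8-week call and add one AE/SAE call at 8 months after the last dose, unless the participant refuses contact. Make footnote a agree with 7.1 on who gets the Early Discontinuation Visit and call, and settle whether the 8-week call has an upper limit.
2. **SAP 7.7.2.** Beside the percentages, report TEAEs and TESAEs per 100 participant-years of actual AE collection, as 7.7.2.4 does for MACE. State, by arm, for whom ascertainment stopped short of 8 months, including those cut off by termination. Enrolment is closed, so this part is the most readily available; the extra call helps only those whose 8 months have not yet run out.

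The cost is one extra call per early leaver, some of them unanswered, slightly later data closure, and an added column in the AE tables. With so few participants the rates will be imprecise and should be read descriptively.
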